### Secondary Objective(s):

To compare 3-week changes in mean glucose and glycemic variability from continuous glucose monitoring (CGM), body weight, waist circumference, fasting GLP-1/PYY level, fasting SCFAs, breath hydrogen and microbiota composition between subjects with pre-diabetes consuming either 30g of WF or 16g of placebo of 'control' carbohydrate (maltodextrin).

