## SUMMARY

**Rationale:** Dietary fibre intake is usually lower than recommended and dried vegetable can be a useful additional source. This may improve glucose metabolism by changes in microbiota composition.

**Objective:** To study the effect of WF Fibre on (continuous) glucose metabolism and potential underlying mechanisms, body weight and waist circumference, microbiota composition and fasting GLP1/PYY, in subjects with pre-diabetes.

**Study design:** Randomised placebo controlled single-blind parallel study

**Study population:** Human volunteers with pre-diabetes (n=60)

**Intervention (if applicable):** One group receives daily a dose of 30g of WholeFiber (WF fibre) and the other group 16g maltodextrin (placebo) for 21 days.

**Main study parameters/endpoints:** Changes in fasting insulin and HOMA-ir are the primary outcomes of the study. Changes in mean glucose and glycemic variability from continuous glucose monitoring, body weight, waist circumference, microbiota composition, breath hydrogen, GLP-1/PYY and SCFAs are the secondary outcomes.

**Nature and extent of the burden and risks associated with participation, benefit and group relatedness:** The intervention is therapeutic for half of the participants and non-therapeutic to the other half of the participants. The risk associated with the participation is negligible and the burden can be considered as minimal. At screening the following measurements and questionnaires will be taken: inclusion and diabetes risk score questionnaire (1x) food frequency questionnaire for fibre intake (1x), height (1x), weight (1x), fasting blood glucose (finger prick). During the intervention period over 3 weeks, with an additional 2 week run-in period and a 2 week wash-out period, subjects will take dietary supplements on the morning of each day of the intervention period, and come to the university on 4 occasions. During this 7 week period the following measurements will be taken: body weight (3x), fasting blood sample (2x), fasting breath sample (2x), continuous glucose monitoring (28 days), faecal samples (4x), wellbeing diary (49 days).

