This study will show whether WF can affect insulin resistance, continuous glucose metabolism and/or the microbiome during a three week period in subjects with elevated risk for developing type 2 diabetes mellitus. This will provide more insight in the potential health effects of a dried vegetable fibre and leads for the potential underlying metabolic changes including microbiota changes.

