### 3. STUDY DESIGN

The study is designed as a single blind, randomised placebo controlled parallel trial in which 2 groups of 30 subjects receive either 30g of WF or 16g of control carbohydrate (maltodextrin, in iso-caloric amount) for a period of 3 weeks (21 days). To reduce potential gastrointestinal side effects of WF, the study will start with a 2 week run-in period during which time WF will be taken at 15g/day for 2 weeks before the actual intervention starts. The control arm will receive MD 8g/day during this period, an iso-caloric amount. The study schedule is summarized below. During the pre-study screening visit a fasting blood glucose measurement will be done using finger-prick and the Dutch diabetes risk score (DRS) will be assessed (<http://www.kijkopdiabetes.nl/professionals/diabetes-risicotest-3>).

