**Table 1. Study schedule VEZEL studie**

	Pre study screening	Before run-in	Run-in 14 days		Intervention 21 days		Wash-out 14 days		
		Day -17	Day -14		Day 1		Day 22		Day 35
Visit number →	1	2			3		4		
Home visit number →			1						2
Activity									
Informed consent	X								
Health questionnaire	X								
Diabetes risk score	X								
Finger prick (fasting glucose)	X								
Food frequency questionnaire	X								
Wellbeing diary			X	X	X	X	X	X	X
Handing out study sachets			X		X				
Return study sachets – compliance check					X		X		
Fasting blood sampling		X					X		
Stool collection			X		X		X		X
Fasting breath sample		X					X		
Continuous glucose monitoring		X	X	X until day -3	X	X until day 14			
Body weight / Waist circumference	X	X			X		X		
Body height	X								
Breakfast	X	X					X		
Post study screen									X
End of trial									X

X: CGM will be placed on the upper arm, device works for 14 days

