#### 8.4 Details on measurements

All measurements will be done using validated methods developed for their purpose, and by experienced laboratories.

During screening, capillary blood sampling will be used for determination of fasting blood glucose using HemoCue B-glucose device (HemoCue AB, Ängelholm, Sweden).

During the intervention fasting insulin and fasting glucose will be measured in serum and NaF-plasma, respectively, as obtained by venepuncture, by Laboratory Clinical Chemistry of ZGV Hospital Ede. HOMA-ir will be calculated from fasting glucose and insulin levels using software from Matthews et al. (1985) (<https://www.dtu.ox.ac.uk/homacalculator>). For GLP-1 and PYY measurements blood will be collected in tubes with aprotinin.

Abbott's FreeStyle Libre Flash will be used as CGM (see Bolinder et al, 2016). It includes a very tiny glucose sensor worn under the skin and connected to a water resistant, plastic on-body patch the size of a coin. The sensor remains inserted for max. 14 days and does not require fingerstick calibrations. The sensor can be inserted by the subject

him/her-self. To obtain readouts a reader device is being used which is held near the sensor patch. The results (glucose value, trend and graph of last eight hours) can be seen immediately (in this case the screen will be covered for the participants) or downloaded to PC software. EasyGV software will be used to assess measures of glycemic variability (Hill et al., 2011) (m-value, mean amplitude of glycaemic excursions, lability index, average daily risk range, j-Index, low blood glucose index and high blood glucose index, continuous overall net glycemic action, mean of daily differences, glycaemic risk assessment diabetes equation, mean average glucose).

Body weight will be measured to the nearest 0.1 kg. Body height will be measured to the nearest 0.1 cm. Waist circumference will be measured to the nearest 0.5 cm.

Microbiota analysis will be performed by the WU Laboratory of Microbiology on faecal samples essentially as described previously (Salonen et al., 2014) with the modification that extracted DNA will be subject to next generation 16S rRNA and/or metagenomic sequencing as described (Korpela et al 2016; Li et al 2016).

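### CGM recording ends at Day 14 of the 21 full-dose days, so the schedule cannot deliver the 3-week CGM change promised in the secondary objective

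*Protocol*

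**What the plan says.** The Secondary Objective in section 2 is "To compare 3-week changes in mean glucose and glycemic variability from continuous glucose monitoring (CGM", together with weight, waist, gut hormones, SCFAs, breath hydrogen and microbiota. Section 1 likewise says that the study will show whether the product affects "continuous glucose metabolism and/or the microbiome during a three week period".

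Section 3 sets the full dose "for a period of 3 weeks (21 days"; in Table 1 this is Day 1 to Day 21, with the closing visit (Visit 4) on Day 22. Before that, "WF will be taken at 15g/day for 2 weeks before the actual intervention starts", with a matching half amount of maltodextrin in the control arm.

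Table 1 gives CGM in two blocks: one from Day -17, ending at Day -3, and one from Day 1, ending at Day 14. Its footnote says that the "device works for 14 days". Section 8.4 agrees: "The sensor remains inserted for max. 14 days". The Summary gives the total as "continuous glucose monitoring (28 days".

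No CGM is marked at Day 22 in Table 1, and section 8.3 lists none among the measurements after the 21 days. Section 10.2 analyses CGM by methods similar to those for the primary outcome, which section 10.1 defines as ANCOVA of the end-line value with the baseline value as covariate. It does not say which CGM days are baseline and which are end-line.

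**The concern.** An objective worded as a 3-week change needs observations that reach the end of week 3. For CGM the last observation comes at the end of week 2 at full dose. The second sensor also starts on the day the product goes from 15 g to 30 g, so its average includes the first days at the new dose.

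The other outcomes in the same sentence (weight, waist, fasting GLP-1/PYY and SCFAs, breath hydrogen, stool microbiota) all have a measurement at Day 22, as do fasting insulin and HOMA-ir. CGM is the exception. A report that followed the objective's wording would present a 2-week result under a 3-week label, beside end-of-treatment measures taken about a week later.

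The baseline side has a related weakness. Most of the first sensor's wear falls after run-in product has started, and that product already differs between the arms. If the whole sensor were used as baseline, the covariate could already carry part of the treatment effect, and adjusting for it could remove some of the difference being estimated.

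**Working it through.** **Inputs.** CGM blocks, visit days and sensor life: Table 1 and its footnote. Sensor life again: section 8.4. Length and amount of run-in and intervention: section 3. Total CGM days: Summary.

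**1. Reproduce the protocol's own total.**
- Sensor 1, Day -17 to Day -3: -3 - (-17) = 14 elapsed days.
- Sensor 2, Day 1 to Day 14: 14 - 1 + 1 = 14 days.
- Sum: 14 + 14 = 28 days, as the Summary states.

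Table 1, its footnote, section 8.4 and the Summary therefore agree. The short second block is the intended schedule and not a damaged table, and a third sensor would not fit within 28 days.

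**2. Coverage of the full-dose period.**
- Full-dose days: Day 1 to Day 21 = 21.
- Covered by CGM: Day 1 to Day 14 = 14, and 14/21 = 67%.
- Not covered: Day 15 to Day 21 = 7, and 7/21 = 33%.

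**3. Sensitivity to how the days are counted.** If sensor life is taken as 14 × 24 hours from the Day 1 visit, recording ends on Day 1 + 14 = Day 15. That is still 22 - 15 = 7 days before Visit 4. Whether the calendar has a Day 0 does not change this.

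**4. The baseline sensor.** Run-in product starts on Day -14.
- Before product: Day -17 to Day -15 = 3 calendar days.
- On run-in product: Day -14 to Day -3 = 12 calendar days, or about 11 if counted as elapsed time.
- Both ends counted, that is 3 + 12 = 15 calendar days, of which 12/15 = 80% are on run-in product.

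**5. Can one sensor reach the end of treatment?** A 14-day sensor whose last full day is Day 21 must start on Day 21 - 13 = Day 8. Counted as 14 × 24 hours it ends on Day 8 + 14 = Day 22, the day of Visit 4. Section 8.4 already provides for insertion at home: "The sensor can be inserted by the subject" without staff.

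**The case against.** **"3-week" is a loose label for the intervention phase.** There is something in this. The change in fasting insulin is also called a 3-week change, although blood is drawn on Day -17 and Day 22, more than five weeks apart. But the looseness there lies at the start of the interval; the end point is still after three weeks at full dose. For CGM the end point itself is missing, and the last third of the period is unobserved.

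**A SAP can define the window.** It can choose among recorded days, for example Days 8-14, and so drop the first days at the new dose. It cannot supply Days 15-21. The mismatch lies between objective and schedule, not in detail left for later.

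**There are glucose data at the end.** Fasting venous glucose is taken on Day 22, so it would be wrong to say that no glucose data exist. One fasting value does not give CGM mean glucose or glycemic variability.

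**A reader might infer that the CGM result understates the effect by a known amount.** The documents do not support that. Section 1 sketches a chain from microbiota through SCFAs to gut hormones, but says the mechanisms are not fully understood and gives no time course. By Day 1 subjects have already taken product for 14 days. Suppose, purely as an assumption, that the effect follows 1 - 0.5·exp(-t/τ) from Day 1. The Day 1-14 mean is then about 89%, 80% or 77% of the modelled Day 21 effect for τ = 3, 7 or 14 days; with an immediate effect it is 100%. The 50% starting level and τ are both invented, so these figures show only how far the answer depends on the assumption.

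**A reader might also infer that a planned link between CGM and the Day 22 samples is broken.** Section 10.2 plans no joint analysis. The supportable statement is that the measures are not concurrent.

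**Conclusion.** The point holds as a contradiction between the stated CGM objective and the measurement schedule. CGM covers 14 of 21 full-dose days (67%) and none of Days 15-21. What the schedule can deliver is the CGM outcome over the first 2 weeks at full dose, ending about a week before the Day 22 measures. This rests only on the protocol's day counts and does not depend on any assumed time course.

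If the effect is still developing after Day 14, the Day 1-14 mean would be smaller than the effect at 3 weeks. The size of any such loss cannot be derived from the protocol and may be zero. The baseline also needs fixing, since only 3 days of the first sensor precede run-in product and no baseline window is named.

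The matter is confined to one group of secondary outcomes. Fasting insulin, HOMA-ir and the sample size calculation are unaffected. It should be corrected, but it does not threaten the trial's main conclusion.

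**What to change.** **Preferred.** In Table 1, hand out the second sensor at Visit 3 (Day 1), have the subject insert it on Day 8, and read it at Visit 4 (Day 22). Define the CGM end-line as Days 8-21, the last 14 days at full dose. The objective can then keep its 3-week wording, with the window stated.

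**If Day 1 placement is kept.** Restate the Secondary Objective in section 2, and the matching sentence in section 1, as the change in CGM mean glucose and variability over the first 2 weeks at full dose.

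**In either case.** Define the CGM baseline as Day -17 to Day -15, before run-in product starts, and name the baseline and end-line days in section 10.2, so that the Summary, section 2, Table 1 and section 10.2 agree.

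**Cost.** Moving the sensor needs one changed row in Table 1 and a participant instruction, with the same planned number of sensors and visits. The downside is some failed or late insertions at home, which may call for a few spare sensors or telephone support, and the need to keep the reader screen covered when no staff are present. The 3-day baseline is shorter and therefore noisier than a whole-sensor mean; as an ANCOVA covariate that costs some precision, but it avoids adjusting for days already on product. Restating the objective costs only wording, but gives up CGM information on the last week of treatment.

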### 3. STUDY DESIGN

The study is designed as a single blind, randomised placebo controlled parallel trial in which 2 groups of 30 subjects receive either 30g of WF or 16g of control carbohydrate (maltodextrin, in iso-caloric amount) for a period of 3 weeks (21 days). To reduce potential gastrointestinal side effects of WF, the study will start with a 2 week run-in period during which time WF will be taken at 15g/day for 2 weeks before the actual intervention starts. The control arm will receive MD 8g/day during this period, an iso-caloric amount. The study schedule is summarized below. During the pre-study screening visit a fasting blood glucose measurement will be done using finger-prick and the Dutch diabetes risk score (DRS) will be assessed (<http://www.kijkopdiabetes.nl/professionals/diabetes-risicotest-3>).

**Table 1. Study schedule VEZEL studie**

	Pre study screening	Before run-in	Run-in 14 days		Intervention 21 days		Wash-out 14 days		
		Day -17	Day -14		Day 1		Day 22		Day 35
Visit number →	1	2			3		4		
Home visit number →			1						2
Activity									
Informed consent	X								
Health questionnaire	X								
Diabetes risk score	X								
Finger prick (fasting glucose)	X								
Food frequency questionnaire	X								
Wellbeing diary			X	X	X	X	X	X	X
Handing out study sachets			X		X				
Return study sachets – compliance check					X		X		
Fasting blood sampling		X					X		
Stool collection			X		X		X		X
Fasting breath sample		X					X		
Continuous glucose monitoring		X	X	X until day -3	X	X until day 14			
Body weight / Waist circumference	X	X			X		X		
Body height	X								
Breakfast	X	X					X		
Post study screen									X
End of trial									X

X: CGM will be placed on the upper arm, device works for 14 days

## 4. STUDY POPULATION

### 4.1 Population (base)

Sixty non-diabetic men and women aged 40-75, at elevated risk for type 2 diabetes, will be recruited regionally from the general population.

### 4.2 Inclusion criteria

In order to be eligible to participate in this study, a subject must meet all of the following inclusion criteria:

- Age 40-75 yr
- Fasting blood glucose between 5.6 and 6.9 mmol/L (pre-diabetes according to American Diabetes Association 2016)
- Or fasting blood glucose between 5.0 and 5.6 mmol/L and diabetes risk score (DRS)  $\geq$  9.

### 4.3 Exclusion criteria

A potential subject who meets any of the following criteria will be excluded from participation in this study:

- Having a history of medical or surgical events that may significantly affect the study outcome: IBS or IBD patients,
- Medical drug use: for diabetes
- Medical drug use: antibiotic use within 3 months of the study screenings day or chronic use of antacids
- Mental status that is incompatible with the proper conduct of the study
- Reported unexplained weight loss or weight gain of > 5 kg in the month prior to pre-study screening
- Reported slimming or medically prescribed diet
- Reported vegan or macrobiotic life-style
- Consumption of pre-probiotics or fibre supplements as of 1 month before the screening
- Sensitive to medical skin adhesives
- Not willing or afraid to give up blood donation during the study
- Personnel of Wageningen University, department of Human Nutrition, their partner and their first degree relatives
- Current participation in other research from the Division of Human Nutrition
- Not having a general practitioner

### 4.4 Screening visit

After an evening visit to the research centre for an information session about the study, interested participants will be invited for a subsequent morning visit to the research centre where fasting blood glucose (finger prick), body height, weight and waist circumference will be measured and 2 questionnaires will have to be filled out, followed by a small breakfast. Informed consent form will be handed out at the information session, and asked to be signed during the screening visit.

#### 4.5 Sample size calculation

The sample size calculation for the study is based on results from literature (Guess et al., 2016), where a mean within-person reduction in fasting insulin of 37 pmol/L was observed, with t-statistic of 2.45 and  $n=7$  equal to an effect size of 0.92 ( $=t/\sqrt{n}$ ). A recent intervention study from our group showed that subjects at risk for diabetes had a mean fasting insulin of 85 pmol/L, with SD 50 mmol/L, and  $SD_{\text{change from baseline}}$  of 37 pmol/L (Duijzer et al, 2017). Based on an effect size of 0.92 as per Guess et al, and  $SD_{\text{change}}$  of 37 pmol/L in a parallel design, 40 (two times 20) subjects will be needed to achieve 80% power at a two-sided alpha of 5% (G\*Power 3.1.9.2 T-test, two independent means, reduction of 34 pmol/L in intervention and 0 pmol/L in control group). To allow for a smaller effect size of 0.78 based on an estimated reduction of 29 pmol/L instead of 34 pmol/L, 54 (two times 27) subjects will be needed. To account for potential drop-out (10%) 60 (two times 30) subjects will be randomised in the study.

## **5. TREATMENT OF SUBJECTS**

### **5.1 Investigational product/treatment**

WF fibre is a product with very high levels of prebiotic dietary fibres (~85%): inulin, pectin, hemi-cellulose and cellulose. The dose will be 30g product per day, corresponding with approximately 25g fibre and 3.5 gram other macro-nutrients (proteins, sugars, organic acids) and 1.5g water per day. The energy content will be ~ 2 kcal/g for fibres and 4 kcal/g for others, i.e. 64 kcal per day.

The 'control' arm will receive 16 g of maltodextrin per day, which will provide with 4 kcal/g also 64 kcal per day. Maltodextrin is a polysaccharide derived from starch. It has been used as placebo in an inulin trial before (DeWulf et al., 2013).

### **5.2 Use of co-intervention (if applicable)**

Medication other than mentioned at the Exclusion criteria is allowed during the study. Subjects will be instructed to maintain their habitual lifestyle.

With respect to the visit to the study site, the subjects are asked to remain fasting (no eating or drinking other than water, after 21.00 hr).

## **6. INVESTIGATIONAL PRODUCT**

### **6.1 Name and description of investigational product(s)**

WholeFiber™ is a high fibre product consisting of mainly inulin, some pectin and hemicellulose and cellulose that is derived from chicory roots. Besides dietary fibres, it contains low levels of proteins (5%), fat (<1%), mono- and disaccharides (3%), organic acids (2%) and minerals (2%). Chicory roots have a long history of safe use for coffee substitute, 'witlof', inulin extraction and their toxicological evaluation has been reported and states that there were no observed adverse effects and the NOAEL for the extract is 1000 mg/kg/g administered orally for 28 days (Schmidt et al., 2007). The product will be provided to the participants in a granulated form that highly palatable and can easily be mixed with yoghurt or other semi-liquid food products.

Maltodextrin will be provided as a powder and obtained from a commercial provider (Body&Fit Pure Maltodextrin).

### **6.2 Summary of findings from non-clinical studies**

Not applicable.

### **6.3 Summary of findings from clinical studies**

Not applicable.

### **6.4 Summary of known and potential risks and benefits**

Not applicable.

### **6.5 Description and justification of route of administration and dosage**

The subjects will be instructed to add WF or maltodextrin to their yoghurt

### **6.6 Preparation and labelling of Investigational (Medicinal) Product**

WF fibre will be delivered to the test site by the sponsor and will be stored at recommended condition. The design, production, and delivery of the test product WF fibre will be performed by the sponsor. Both products will be packed by the research team and labelled A and B.

### **6.7 Drug accountability**

WF fibre will be delivered to the test site at Wageningen University by WholeFiber Holding INC. Maltodextrin will commercially obtained by the research team. Study personnel on site will supervise and register the compliance of taking the products.

## 7. NON-INVESTIGATIONAL PRODUCT

Not applicable.

## 8. METHODS

### 8.1 Study parameters/endpoints

#### 8.1.1 Main study parameter/endpoint

Fasting insulin and HOMA-ir (homeostatic model assessment of insulin resistance, derived from fasting insulin and fasting glucose levels).

#### 8.1.2 Secondary study parameters/endpoints (if applicable)

- Continuous Glucose Monitoring (CGM): mean glucose and glycemc variability
- Body weight
- Waist circumference
- Microbiota composition
- Breath hydrogen
- Fasting GLP-1/PYY
- Fasting SCFA
- Adverse events (bloating, belching, flatulence)

